9.2 SAMPLE SIZE DETERMINATION

- Primary Efficacy Endpoint(s):

H1 (alternative): Providers in the CDS and CDS-E strategy arms will reduce their likelihood of prescribing opioids for patients following extractions more than providers in the SP arm.

H1 patient-level endpoint: A binary code (0/1) indicating that a provider prescribed an opioid medication to the patient on the date of the index extraction encounter.

Sample size and power: Preliminary data from 2018 indicates there will be 6,900 unique patients age 16 and higher with a permanent tooth extracted by 51 dental providers in the baseline period and also an estimated 6,900 unique patients age 16 and higher with a permanent tooth extracted by 51 dental providers during the intervention period. The study analysis is expected to have at least

this many patients. Fully 40% of encounters in the baseline period with patients having a permanent tooth extraction included a prescription for opioid use, and the provider-level opioid use $ICC=0.3$. Assuming the use of a generalized linear mixed model, with $\alpha=0.05$, two-sided tests, the planned analysis for H1 can detect a differential raw reduction of 23% from pre- to post-intervention opioid prescribing when comparing CDS or CDS-E patients (40% with opioid prescriptions pre-implementation to 15% post-implementation) to SP patients (40% with opioid prescriptions pre-implementation to 38% post-implementation) with 80% power. Power calculations were conducted with PASS v11 (NCSS Software).

- Secondary Efficacy Endpoint(s):

H2 (alternative): Providers in the CDS and CDS-E strategy arms will increase their likelihood of recommending NSAIDs and/or APAP at the extraction encounter and not prescribing opioids for patients following extractions more than providers in the SP arm.

H2 endpoint: A binary code (0/1) indicating that a provider both 1) prescribed or recommended in the treatment plan use of non-opioid analgesics and 2) did not prescribe an opioid prescription on the date of the extraction encounter.

Sample size: This analysis will use the same analytic sample described for H1. The rate is unknown but will be lower than the percentage not prescribing opioids in H1 (60%) since the endpoint is a composite requiring no opioid prescription and also recommendation of non-opioid analgesic.

H3 (alternative): Patients will report higher levels of the extent of shared decision making in the CDS-E arm than the CDS or SP arms.

H3 endpoint: Mean of the 3-item composite of adapted Collaborate Shared Decision Making score reported by the patient within 3-6 days of the extraction encounter.

Sample size: Survey materials will be sent to 1520 patients. The historical response rate for dental research surveys at the organization is 79%, yielding surveys returns from 1200 patients.

H4 (descriptive): Compare patient report of average pain in the week following extraction across the 3 study arms.

H4 endpoint: Mean pain rating in the 3-6 days since the extraction encounter, self-reported by patients within 3-6 days of the extraction encounter.

Samples size: This analysis will use the same analytic sample from the patient survey as described in H3.

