6.3 MEASURES TO MINIMIZE BIAS: RANDOMIZATION AND BLINDING

The randomization of providers to study arm will utilize stratification on baseline factors in order to balance key provider factors evenly across study arms. Specific stratification factors to be utilized will be outlined in the Statistical Analysis Plan. Providers will be randomly allocated 1:1:1 through a computer-generated program to either Standard Practice, CDS, or CDS-E. Patients will be exposed to the intervention to which their provider has been randomized based on the provider they see at the index extraction visit. Systematic sampling with a variable sampling ratio by provider will be used to identify a sample of patients to receive the post-visit survey. This sampling strategy will approximate stratified random sampling and ensure roughly equal counts of patient surveys by provider and study arm. At each patient encounter, the CDS Web service will collect patient level data from the EHR (e.g., medical conditions, current medications, social history). Providers assigned to the CDS or CDS-E arms will be able to access the information using the CDS tool. Providers assigned to the control arm will continue to use their usual methods to assess and address pain management for dental procedures without any effort to influence their prescribing of analgesics following the dental extraction. They will not be shielded from other outside influences.

At the index encounter (the initial patient visit for a dental extraction during the intervention period where all the study criteria are met), the patient is assigned a unique study identifier that is used to link patient encounter data over time. All index and subsequent encounter data for eligible patients are stored in a limited de-identified analysis dataset.

In order to minimize contamination across study arms, only providers in the CDS or CDS-E arms will be able to access the clinical decision support. Similarly, patients who receive care from providers in the CDS-E arm will have access to supplemental patient education. As such, both groups will know their assignment. The study team will not disclose the study's purpose, objectives, or outcomes measures directly to patients until after the encounter or after the participant has been surveyed about their experience, if selected.

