9.4 STATISTICAL ANALYSES

9.4.1 GENERAL APPROACH

Baseline characteristics of study participants will be summarized with mean and standard deviation for interval data and proportions for categorical data. General and generalized linear mixed models will be used to test study arm differences in endpoints. Models will include terms for study arm, time (for models assessing change from pre- to post-intervention), and their interaction. Covariates to be included in models will be described in the Manual of Procedures (MOP). A random intercept for provider will be included in models to account for the cluster-randomized design with providers as the unit randomized. Differential change will be compared for each study arm via a series of planned contrasts. Study arm contrasts will be tested at alpha=0.05 and all tests will be two-sided. Model-predicted means and proportions along with 95% confidence intervals will be used to assess the magnitude, direction, and precision of intervention effects.

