9.4.2 ANALYSIS OF THE PRIMARY EFFICACY ENDPOINT(S)

H1: Providers in the CDS and CDS-E strategy arms will reduce their likelihood of prescribing opioids for patients following extractions more than providers in the SP arm.

Analysis plan: Hypothesis H1a posits that patient encounters at which extractions are performed by dental providers in the CDS and CDS-E arms will have a larger reduction in the likelihood of receiving an opioid prescription at the index encounter than patient encounters in the SP arm when comparing independent samples of patient encounters before the implementation to patient encounters following the implementation. A generalized linear mixed-model regression with a logit link and binomial error distribution will be used to test the effects of the implementation strategies. The patient-level endpoint (patient received an opioid prescription at the index encounter) is coded as a binary outcome variable. This endpoint will be predicted by 2 fixed-effects terms for study arm of CDS (CDS vs. SP) and CDS-E (CDS-E vs. SP), year in which the patient has an extraction (post or pre-implementation), and by interaction terms of study arm and year. A random intercept for provider will be included in the model to accommodate the cluster-randomized design with providers as the unit randomized. Additional covariates to be included will be described in the MOP. Model-predicted proportions and confidence intervals of opioid prescribing will be summarized by time and study arm jointly. Contrasts will estimate differential reduction in the endpoint comparing CDS vs. SP and CDS-e vs. SP. This analysis will be conducted on the Intention to Treat Analysis Dataset.

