9.4.5 BASELINE DESCRIPTIVE STATISTICS

The cluster-randomized design of the trial increases the probability of study arm imbalance on patient factors. Baseline patient factors will be summarized and compared across the three study arms using descriptive statistics (mean, SD, median, interquartile range, proportion) and confidence intervals. Results of statistical tests conducted on patient factors by study arm will not be used to inform covariate adjustment. Rather, in a-priori sensitivity analyses the models described in the analysis plan will include patient covariates of age, race, and public pay status.

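### The 80% power for a 23-point differential reduction in Section 9.2 does not belong to the random-intercept-only H1 model in Section 9.4.2, and the between-period correlation that links them is not stated

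*Combined protocol and SAP*

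**What the plan says.** Section 9.2 takes 51 providers, 6,900 patients in each period, a 40% baseline opioid rate, a provider-level ICC of 0.3 and a two-sided alpha of 0.05. "Assuming the use of a generalized linear mixed model", it states that "the planned analysis for H1 can detect a differential raw reduction of 23% from pre- to post-intervention opioid prescribing" at 80% power. The scenario is 40% falling to 15% in an intervention arm and 40% falling to 38% in SP. PASS v11 is named, without the procedure or any correlation between a provider's two years.

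Section 9.4.2 defines the test. The endpoint is predicted by arm, by year and "by interaction terms of study arm and year", with pairwise contrasts of CDS and CDS-E against SP. On clustering it says: "A random intercept for provider will be included in the model to accommodate the cluster-randomized design". Section 9.4.1 says the same for the models generally: "A random intercept for provider will be included in models to account for the cluster-randomized design". Neither section names a provider-by-period effect. What they defer to the Manual of Procedures is covariates. Section 9.4.3 reuses the strategy for H2.

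Section 9.4.5 adds that "in a-priori sensitivity analyses the models described in the analysis plan will include patient covariates of age, race, and public pay status".

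**The concern.** A power figure should describe the test that will be run. A provider intercept that is common to both years cancels from a pre-to-post change, so under the written model the ICC of 0.3 costs the interaction test almost nothing. A detectable difference as large as 23 points is therefore unexpected for that model. It suggests either a calculation for a different comparison or a between-period correlation below 1.

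The second possibility matters beyond Section 9.2. If a provider's rate moves between years for reasons particular to that provider, the change contrast carries provider-by-period variance that a random intercept alone leaves out. With about 135 patients per provider per period, binomial noise is small and the omitted part can dominate. The primary test would then reject too often. The sensitivity analyses in Section 9.4.5 add only patient covariates and keep the same random effects, so they would not reveal it.

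**Working it through.** **Inputs.** From Section 9.2: 51 providers, 6,900 patients per period, ICC 0.3, two-sided alpha 0.05, rates 40%/15% and 40%/38%. From Section 4.1: 1:1:1 allocation, so 17 providers and 2,300 patients per arm per period, and m = 6,900/51 = 135.3 patients per provider-period. CAC is not given and is an assumption throughout. Provider volumes are taken as equal unless stated.

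**1. Reproducing 80%.** Compare post-period rates only, 38% against 15%.
- Design effect = 1 + (135.3 − 1) × 0.3 = 41.29. Effective n per arm = 2,300/41.29 = 55.7.
- Unpooled SE = √[(0.38×0.62 + 0.15×0.85)/55.7] = 0.0807.
- Power = Φ(0.23/0.0807 − 1.96) = 81.3%. With the pooled null variance it is 79.4%.

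So the inputs reproduce the stated figure as a post-only comparison. The match needs equal volumes: at an assumed volume CV of 0.5, the design effect 1 + ((1 + CV²)m − 1) × 0.3 = 51.4, effective n is 44.7 and power is 70–72%.

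**2. Difference in change, same inputs.** With v = p(1 − p), the variance per arm is

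[ICC(v₁ + v₂) − 2·CAC·ICC·√(v₁v₂) + (1 − ICC)(v₁ + v₂)/m]/17,

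where v₁ = 0.24 (pre) and v₂ = 0.1275 (post, 15%) or 0.2356 (post, 38%). The SE is the root of the sum over two arms. Power = Φ(0.23/SE − 1.96).

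| CAC | SE | Power for 23 points |
|---|---|---|
| 0.5 | 0.0886 | 74% (71% with t, 32 df) |
| 0.576 | 0.0821 | 80% (77.5% with t) |
| 0.8 | 0.0590 | 97% |
| 1 | 0.0238 | >99.9% |

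Power of 80% is reached at CAC 0.58 by the normal approximation and 0.60 with t on 32 df.

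**3. Detectable difference at CAC 1.** The SE depends on the active arm's post rate, so it must be solved at the effect itself. At a post rate of 33.2%, v₂ = 0.2218.
- Active arm: [0.3×0.4618 − 0.6×√(0.24×0.2218) + 0.7×0.4618/135.3]/17 = 0.000147.
- SP arm: 0.000145.
- SE = √0.000292 = 0.0171, and 2.80 × 0.0171 = 0.048.

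The detectable difference is about 4.8 points. Using the SE of the 23-point scenario instead (2.80 × 0.0238 = 6.7 points) overstates it.

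In a simulation of 150 trials per setting, fitting the random-intercept logistic model at CAC 1, the 23-point scenario was rejected in 100% of trials and a 5-point difference in 81%.

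**4. False positives of the written model.** Take 40% in every cell. For each arm (before dividing by 17), the change has variance 2×0.24×0.3×(1 − CAC) + 2×0.24×0.7/135.3 = 0.144(1 − CAC) + 0.00248. A random intercept alone accounts only for the second term. The ratio of true to model SE is R = √[1 + 0.144(1 − CAC)/0.00248], and the rejection rate is 2Φ(−1.96/R).

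| Assumed CAC | R | Rejection of a true null |
|---|---|---|
| 1 | 1.00 | 5% |
| 0.95 | 1.97 | 32% |
| 0.8 | 3.55 | 58% |
| 0.58 | 5.04 | 70% |

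A simulation with the fitted logistic model (1,000 trials per setting, 17 providers per arm) gave 5.9%, 32.8%, 58.4% and 69.5%. At CAC 0.8 the mean model SE was 0.101 and the empirical SD 0.367. The simulation sets CAC on the logit scale and the closed form on the proportion scale, so the two agree in pattern but are not strictly like for like.

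**The case against.** Under the model as written, the stated figure is conservative, and the sample follows from the providers and patient volume expected from 2018 data, so no enrolment decision turns on it. That stands. A reader might infer that the trial is underpowered, or that Section 9.2 contains an arithmetic error. The documents support neither: at CAC 1 power is far above 80%, and the inputs do yield 79–81% for a recognisable comparison.

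A reader might also conclude that Section 9.2 simply is a post-only calculation. The numbers fit, but the PASS procedure is not named, so this is an inference.

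The false-positive question concerns Section 9.4.2 and would exist whatever Section 9.2 said. It also rests on a CAC that the documents do not give, and at CAC 1 the test is close to nominal. This stands too, so the rates in step 4 illustrate and do not predict. It is tempting to cite the statement on SP providers in Section 6.3, "They will not be shielded from other outside influences", as evidence of drift. It is not: influences common to all providers are absorbed by the year term and the SP comparison, and inflation needs drift particular to individual providers.

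Finally, naming a random intercept does not strictly exclude other random effects, and Section 6.3 refers to a Statistical Analysis Plan for stratification factors that this text does not list. Intercept-only remains the natural reading, since nothing on the random effects is deferred.

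**Conclusion.** The concern holds as a mismatch between power figure and model. For the arm-by-year test with only a provider random intercept, the stated inputs give over 99% power at 23 points and a detectable difference of about 5 points. For any difference in change, 80% at 23 points needs a CAC of about 0.58–0.60, which is unstated and which the written model does not allow. This part rests only on the inputs in Section 9.2, equal provider volumes and the intercept-only reading.

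The consequence for the primary test is conditional. If CAC is below 1, the planned standard error is too small, and even an assumed 0.95 takes the error rate from about 5% to about 32%. The documents do not establish that CAC is below 1, but neither the model nor the planned sensitivity analyses protect against it. The plan should be changed on this point, although it does not bear on whether the trial can proceed.

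**What to change.** - **Section 9.2:** state the PASS procedure and the between-period correlation actually used, and the assumption about provider volumes. Do not relabel the figure as post-only unless the sponsor's records confirm it. Restate power or the detectable difference for the arm-by-year contrast over a CAC range, for example 0.5 to 1. With equal volumes, power for 23 points is about 71–74% at 0.5, 97% at 0.8 and over 99% at 1.
- **Section 9.4.2, and Section 9.4.3 for H2:** add a provider-by-period random effect, or use a provider-level change analysis, before post-period outcomes are analysed.

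The cost is one recalculation, some rewording and one added variance term, with no change to enrolment or data collection. The downside is wider intervals and possibly a less favourable stated figure. In the 1,000-trial simulation a provider-level t-test on change held false positives at 4.4–5.6%, with power for the 23-point scenario of 100% at CAC 1, 94% at 0.8 and 75% at 0.58 (CAC on the logit scale).

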9.3 POPULATIONS FOR ANALYSES

Patient Encounter Study Population for H1, H2

The analytic denominator for H1 and H2 will consist of up to 16,800 (8400 baseline and 8400 intervention) first extraction encounters of patients aged 16 and higher and linked to a study-eligible provider, and who have a permanent tooth extraction during the year prior or year after the implementation of the strategies.

Patient Study Population for H3, H4

The analytic denominator for H3 and H4 will start with the approximately 8,400 patients who meet the criteria for the analytic denominator during the intervention period for H1 and H2 above. This analytic dataset will be further reduced to the approximately 1,520 patients who are approached to complete and complete a patient survey within 6 days of the index encounter. Of the approximately 1,520 patients approached it is expected that the analysis for H3 and H4 will include data from 1,200 patients.

9.4 STATISTICAL ANALYSES

9.4.1 GENERAL APPROACH

Baseline characteristics of study participants will be summarized with mean and standard deviation for interval data and proportions for categorical data. General and generalized linear mixed models will be used to test study arm differences in endpoints. Models will include terms for study arm, time (for models assessing change from pre- to post-intervention), and their interaction. Covariates to be included in models will be described in the Manual of Procedures (MOP). A random intercept for provider will be included in models to account for the cluster-randomized design with providers as the unit randomized. Differential change will be compared for each study arm via a series of planned contrasts. Study arm contrasts will be tested at alpha=0.05 and all tests will be two-sided. Model-predicted means and proportions along with 95% confidence intervals will be used to assess the magnitude, direction, and precision of intervention effects.

9.4.2 ANALYSIS OF THE PRIMARY EFFICACY ENDPOINT(S)

H1: Providers in the CDS and CDS-E strategy arms will reduce their likelihood of prescribing opioids for patients following extractions more than providers in the SP arm.

Analysis plan: Hypothesis H1a posits that patient encounters at which extractions are performed by dental providers in the CDS and CDS-E arms will have a larger reduction in the likelihood of receiving an opioid prescription at the index encounter than patient encounters in the SP arm when comparing independent samples of patient encounters before the implementation to patient encounters following the implementation. A generalized linear mixed-model regression with a logit link and binomial error distribution will be used to test the effects of the implementation strategies. The patient-level endpoint (patient received an opioid prescription at the index encounter) is coded as a binary outcome variable. This endpoint will be predicted by 2 fixed-effects terms for study arm of CDS (CDS vs. SP) and CDS-E (CDS-E vs. SP), year in which the patient has an extraction (post or pre-implementation), and by interaction terms of study arm and year. A random intercept for provider will be included in the model to accommodate the cluster-randomized design with providers as the unit randomized. Additional covariates to be included will be described in the MOP. Model-predicted proportions and confidence intervals of opioid prescribing will be summarized by time and study arm jointly. Contrasts will estimate differential reduction in the endpoint comparing CDS vs. SP and CDS-e vs. SP. This analysis will be conducted on the Intention to Treat Analysis Dataset.

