4.2 SCIENTIFIC RATIONALE FOR STUDY DESIGN

The cluster-randomized trial design randomizes dental providers to one of three study arms. This design maximizes the number of randomized units (providers) as compared to clinic- level randomization. Cluster randomization with providers as the unit randomized allows for techniques to balance attributes of providers and their patients across study arms. This design also solves the practical issue of providers floating across several clinics and different study arms that would occur in clinic- level randomization. Cluster randomization with providers as the unit randomized also has advantages over patient-level randomization because providers who are exposed to the interventions intermittently may change their usual practices in ways that would not occur naturally. Cluster randomization with providers as the unit randomized also matches the unit of randomization with the level at which the intervention is expected to have an effect, which is at the provider level.

The Standard Practice (SP) arm was selected as a control to reflect care as it is currently performed and to serve as a comparison of secular trends in care, by contrasting such trends in a provider group that does not receive an intervention (SP), with those providers in the two active intervention arms (CDS, CDS-E).

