7 STUDY INTERVENTION DISCONTINUATION AND PARTICIPANT DISCONTINUATION/WITHDRAWAL

7.1 DISCONTINUATION OF STUDY INTERVENTION

Providers should exercise clinical judgment and can at their discretion disregard any information the CDS offers. As such, patients will receive usual dental care, regardless of study arm.

Hospitalizations documented within the HealthPartners electronic health record that occur within a 72-hour window following the index extraction encounter will be chart reviewed for severity and relatedness on a quarterly basis during the intervention period by Co-investigator and/or PI [name]. These hospitalizations rates will be compared at a frequency determined by the DSMB or quarterly whichever is greater.

Based on the relevant data, the study team in consultation with the DSMB would determine whether the study intervention needed to be modified or discontinued.

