9.4.3 ANALYSIS OF THE SECONDARY ENDPOINT(S)

H2: Providers in the CDS and CDS-E strategy arms will increase their likelihood of satisfying the composite endpoint defined by: 1) prescribing or recommending non-opioid analgesics at the extraction encounter and 2) not prescribing opioids at the index encounter for patients following extractions more than providers in the SP arm.

Analysis plan: Hypothesis H2 posits that patient encounters at which extractions are performed by dental providers in the CDS and CDS-E arms will have a larger increase in the likelihood of receiving a prescription or recommendation for non-opioid analgesics and not prescribing opioids at the index encounter than patient encounters in the SP arm when comparing independent samples of patient encounters before the implementation to patient encounters following the implementation. The same analytic strategy used for the primary endpoint will be used for this secondary endpoint and will be conducted on the Intention to Treat Analysis Dataset.

H3 (alternative): Patients will report higher levels of the extent of shared decision making in the CDS-E arm than the CDS or SP arms.

Analysis plan: Hypothesis H3 posits that patients will report higher levels of the extent of shared decision making in the CDS-e arm than CDS or SP arms during the strategies implementation time period. A general linear mixed-model regression with an identity link and normal error distribution will be used to test the effects of the implementation strategies. The patient-level endpoint is the score on the 3-item composite of adapted Collaborate Shared Decision Making, and is considered an interval-level variable. This endpoint will be predicted by 2 fixed-effects terms for study arm of CDS (CDS vs. SP) and CDS-E (CDS-E vs. SP). A random intercept for provider will be included in the model. Additional covariates to be included will be described in the MOP. Model-predicted means and confidence intervals for the endpoint will be summarized by study arm. A contrast will estimate the difference in the mean of the endpoint for patients in the CDS-e arm vs. CDS and SP (pooled). This analysis will be conducted on the Intention to Treat Analysis Dataset.

H4 (descriptive): Compare patient report of mean pain in the week following tooth extraction across the 3 study arms.

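### The H1 and H2 models test the arm-by-period interaction with only a provider random intercept, so the contrasts are judged on patient-level error, and the 80% power in 9.2 is not the power of this model

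*Combined protocol and SAP*

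**What the plan says.** Section 9.4.2 fits a logit mixed model with terms for arm, year and arm by year, and takes CDS vs SP and CDS-E vs SP from the interaction. For clustering it says: "A random intercept for provider will be included in the model to accommodate the cluster-randomized design with providers as the unit randomized". Section 9.4.1 sets the same rule for all models: "A random intercept for provider will be included in models to account for the cluster-randomized design". Section 9.4.3 carries it to H2: "The same analytic strategy used for the primary endpoint will be used for this secondary endpoint".

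No provider-by-period effect, random slope for year, robust variance or degrees-of-freedom rule is stated. Sections 9.4.1 and 9.4.2 defer covariates to the Manual of Procedures, but not random effects. Section 9.4.5 adds only patient covariates, in sensitivity analyses: "the models described in the analysis plan will include patient covariates of age, race, and public pay status".

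Section 9.2 assumes 51 providers, 6,900 patients per period, 40% baseline prescribing and a provider ICC of 0.3. It states that "the planned analysis for H1 can detect a differential raw reduction of 23% from pre- to post-intervention opioid prescribing" with 80% power (40% to 15% vs 40% to 38%). It gives neither a between-period correlation nor the scale of the ICC.

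**The concern.** A random intercept is common to a provider's encounters in both years. It protects a comparison of arms within one period. It does not protect a comparison of changes, because it cancels from each provider's own change (exactly on a linear scale, nearly so on the logit scale). What remains in the error term is binomial sampling of patients, although the randomised units are about 17 providers per arm.

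If providers drift by different amounts for reasons unrelated to the intervention, that variation enters the contrast but not its standard error. Such drift is plausible: the two years are independent patient samples, and section 6.3 says of the control providers, "They will not be shielded from other outside influences". Confidence intervals would then be too narrow, and chance differences in drift could be declared an intervention effect. Separately, section 7.1 says: "Providers should exercise clinical judgment and can at their discretion disregard any information the CDS offers". That makes unequal response plausible when the intervention works. It affects interval width, not type I error.

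**Working it through.** **Inputs from 9.2 and 6.3.** 51 providers allocated 1:1:1, so 17 per arm. 6,900/51 = 135.3 patients per provider per period, and 2,300 per arm per period. ICC 0.3, two-sided alpha 0.05.

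**1. What the stated 80% requires.** SE = 23/(1.96 + 0.84) = 8.2 points.

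**2. Reproducing the 80%.** Two readings do so.

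- *Post-period only, 38% vs 15%.* Design effect = 1 + 134.3 × 0.3 = 41.3. Effective n per arm = 2300/41.3 = 55.7. SE = √[(0.2356 + 0.1275)/55.7] = 8.07 points. Power is 81.3% (79.4% with pooled variance).
- *Change from baseline with between-period correlation r.* Per-provider variance of change = 0.3(a + c − 2r√(ac)) + 0.7(a + c)/135, where a and c are p(1−p) before and after. At r = 0.59 this is 0.0610 for SP and 0.0502 for an intervention arm. SE = √(0.1112/17) = 8.1 points, and power is about 80% on 48 df.

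Both readings contain provider-level error.

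**3. The model as written.** With no provider-level error in the change and ICC 0.3 on the proportion scale, SE = √[0.7 × (0.24 + 0.2356 + 0.24 + 0.1275)/2300] = √(0.7 × 0.8431/2300) = 1.6 points. With ICC 0.3 on the latent scale it is 1.7 points. The difference detectable with 80% power is 2.80 × 1.6 = 4.5 points, or 2.80 × 1.7 = 4.8 points. Power at 23 points is effectively 100%. In simulation of the written model, 40% to 33% vs 40% to 38% (a 5-point differential) had 78% power (latent ICC) or 84% (proportion ICC).

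**4. Type I error if providers' changes differ.** The SD of logit change is assumed, because the documents give none. The latent provider variance is 0.3 × (π²/3)/0.7 = 1.41. The written model was simulated with no effect, 1,500 replicates per SD, Wald z test. The check is a closed form: true SD of the contrast = √(0.096² + 2·SD²/17), where 0.096 is the model's standard error.

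| SD of logit change | SD in provider rate (points) | True SD of contrast (simulated) | Type I error, simulated | Closed form |
|---|---|---|---|---|
| 0 | 0 | 0.095 | 4% | 5% |
| 0.1 | 1.9 | 0.102 | 6% | 6.5% |
| 0.2 | 3.9 | 0.119 | 11% | 11% |
| 0.3 | 5.8 | 0.147 | 20% | 18% |
| 0.4 | 7.7 | 0.171 | 27% | 26% |
| 0.5 | 9.7 | 0.202 | 35% | 34% |
| 0.75 | 14.6 | 0.281 | 49% | 49% |

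The model's own standard error stays near 0.096 throughout. With ICC 0.3 on the proportion scale, the simulated rates are 6%, 19% and 36% at SDs of 0.1, 0.3 and 0.5. With unequal provider volumes (assumed CV 0.8, minimum 6) they are 7%, 26% and 44%. Using a t reference on 48 df without changing the model does not help: 19% at 0.3 and 34% at 0.5.

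**5. Interval width at the planned effect.** With a response SD of 0.5 in the CDS arms only, the true SD of the contrast is 0.171 against a model SE of 0.108, a ratio of 1.6.

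**The case against.** The strongest reply is that the gap in 9.2 does not itself prove that needed error is missing. If the 80% came from the post-only reading, the error counted there is stable between-provider variance, which a pre-post contrast rightly removes. The figure would then merely be conservative. That stands: the gap shows that 9.2 does not describe the 9.4.2 model, while the validity problem rests on the model's structure.

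Second, the inflation depends on an SD the documents do not give, and at SD 0 the test keeps its level. That also stands, and the sizes above are conditional.

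Third, the direct evidence for unequal drift is limited. Section 6.3 speaks of control providers in general. The remark in section 4.2 on "providers floating across several clinics" is an argument against randomising clinics and adds little here. But the plan assumes exactly zero variation in change, and nothing in the documents supports that either.

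Fourth, at the planned effect the conclusion would survive. The conditional log-odds contrast is about −1.54, still 1.54/0.281 = 5.5 SDs from zero in the worst row of the table. The risk lies with null or small effects and with interval width.

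Finally, the Manual of Procedures was not available, nor was any separate SAP of the kind section 6.3 mentions for stratification factors. The point concerns what the reviewed document states.

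**Conclusion.** The concern holds. As written, both primary contrasts, and those for H2, have no provider-level component in their error term, and the 80% in 9.2 is not the power of that model. The omission and the power mismatch are certain on the text. The size of the type I error is conditional: nominal if all providers change equally, about 20% at an SD of logit change of 0.3, and about 35% at 0.5, for 17 providers per arm with equal volumes of 135 per period. No H2 figure can be derived, because 9.2 gives its baseline rate as unknown. This does not show the trial to be underpowered.

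**What to change.** **Model (9.4.1, 9.4.2, and so H2).** For models of change, specify a random provider intercept plus a random provider-by-period effect. A random period slope with unstructured covariance is an alternative. Set degrees of freedom to analysed providers minus estimated provider-level parameters: 51 − 3 = 48 or 60 − 3 = 57 with no other provider-level terms, and fewer after exclusions under section 7.3.

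**Sensitivity analysis and convergence fallback.** Prespecify a provider-level comparison of the pre-post change in proportion prescribed, on the same df. State that equal weights target the average provider, whereas 9.1 is framed by encounter. If the encounter target is to be kept, use the encounter-weighted difference with a delete-one-provider jackknife SE.

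**Section 9.2.** State the assumed between-period correlation and the scale of ICC 0.3, and recompute power for the revised model.

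**Performance.** Under the null, the revised mixed model rejects 4.1%, 6.1% and 5.6% at SDs of 0, 0.3 and 0.5 with equal volumes, and 4.0%, 6.1% and 6.7% with unequal volumes, so a slight excess remains. The equal-weight provider-level t-test rejects 4.4–5.6% and 4.4–6.1%.

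**Cost.** One model term, a df rule and a few sentences, on data already planned. The contrast SE rises by factors of about 1.03, 1.4 and 2.0 at SDs of 0, 0.3 and 0.5. Power at 23 points, from the provider-level t-test on 48 df with equal volumes, is:

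- ICC on the proportion scale: 97%, 89%, 80% and 72% at between-period correlations of 0.8, 0.7, 0.6 and 0.5. It falls below 80% under about 0.59 (0.62 with unequal volumes).
- ICC on the latent scale: 98%, 90%, 85% and 75% at 0.8, 0.6, 0.5 and 0.3.

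On the latent scale the correlation is 1 − SD²/(2 × 1.41), so SDs of 0.3, 0.5 and 0.75 correspond to 0.97, 0.91 and 0.80. Over the range in the table, latent-scale power after the fix is therefore about 98% or more. The encounter-weighted fallback costs more with unequal volumes: 91%, 73% and 65% at latent correlations of 0.8, 0.6 and 0.5.
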